One particularly challenging and sometimes severe complication of bariatric surgery is hyperinsulinemic hypoglycemia [4, 5]. While most commonly associated with roux-en-Y gastric bypass, hypoglycemia has also been observed with sleeve gastrectomy [6]. Post-bariatric hypoglycemia (PBH) in this setting is defined as a documented plasma glucose level below 70 mg/dl in conjunction with symptoms and the relief of symptoms with the normalization of glucose levels. Hypoglycemia typically occurs within 1-3 hours after meals, particularly meals rich in simple carbohydrates, and is not present after prolonged fasting. Plasma insulin concentrations are inappropriately high at the time of hypoglycemia, indicating dysregulation of insulin secretion as an important mechanism [7]. Hypoglycemic symptoms may be autonomic (e.g., palpitations, lightheadedness, sweating) or neuroglycopenic (e.g., confusion,

decreased attentiveness, seizure, loss of consciousness) in nature. Early in the post-operative period, hypoglycemia is usually mild, often associated with dumping syndrome, and effectively treated with low glycemic index diets. Mild, often unrecognized, hypoglycemia is increasingly recognized as a potential contributor to increased appetite and weight regain after surgery [8].

A subset of post-bariatric patients develops very severe hypoglycemia with neuroglycopenia, with **loss of consciousness, seizures and motor vehicle accidents**, typically occurring 1-3 years following bypass. For these patients, a comprehensive multidisciplinary approach is required. Treatment of hypoglycemia, once it develops, requires rapid-acting carbohydrates, such as glucose tablets. Unfortunately, this treatment can contribute to rebound hyperglycemia, triggering further insulin secretion and recurrent hypoglycemia. Thus, initial prevention of hypoglycemia is essential. A cornerstone of therapy is dietary modification, aimed at reducing intake of high glycemic index carbohydrates [20]. Both diet and pre-meal acarbose [21] aim to minimize rapid postprandial surges in glucose which are triggers for glucose-dependent insulin secretion. Continuous glucose monitoring can be helpful to improve patient safety, particularly for those with hypoglycemic unawareness [22]. Additional therapies include octreotide (to reduce incretin and insulin secretion) [23], diazoxide (to reduce insulin secretion) [24], calcium channel blockade (to reduce insulin secretion) [25], gastric restriction or banding (to slow gastric emptying) [26], and providing nutrition solely through a gastrostomy tube placed into the bypassed duodenum [27]. Surprisingly, reversal of gastric bypass is not uniformly successful [5, 10], suggesting the importance of underlying genetics and/or compensatory mechanisms which persist after

surgical reversal. Finally, while pancreatic resection was initially employed for patients with life-threatening hypoglycemia [4, 5], this procedure is not uniformly successful in remitting hypoglycemia and thus is not routinely considered at the present time.

Despite strict adherence to medical nutrition therapy and clinical use of multiple medical options above, usually in combination, patients continue to have frequent hypoglycemia. While hypoglycemia most commonly occurs in the postprandial state, it can also be observed in response to increased activity and emotional stress. Importantly, patient safety is additionally compromised when hypoglycemia unawareness develops with recurrent hypoglycemia. Patients are often disabled by hypoglycemia which occurs multiple times per day, leading to inability to drive or maintain employment, and causing fear of eating and exercise due to potential provocation of hypoglycemic events, cardiac arrhythmias [28], syncope, falls, and seizures. Thus, **there is an urgent need for improved approaches to the treatment of severe hypoglycemia to maintain health, allow optimal nutrition, and improve safety in PBH.**

Glucagon injection therapy is highly effective for treating severe hypoglycemia in patients with PBH. However, this approach is very expensive (average wholesale price of Lilly Glucagon emergency kit was \$181 in 2013, Truven Health Analytics RedBook® Online) if used several times daily (as is needed for some patients), and once standard glucagon powder is reconstituted, it needs to be discarded after 24 hours. Furthermore, use of the standard dose of glucagon in emergency kits (0.5-1 mg) or with continuous infusion [29] can provoke rebound hyperglycemia, triggering further meal-dependent insulin secretion and initiating a roller coaster of recurrent hypoglycemia.

[figure not shown]
The prevalence of this disorder remains uncertain due to both incomplete analysis and recognition [30]. For example, a retrospective study of nationwide registries in Sweden demonstrated that gastric bypass was associated with a low overall rate (<1%), but a 2-7 fold increased risk of hypoglycemia and related confusion, syncope, and seizures[31]. Similar patterns were observed in other retrospective studies with patient self-report [20, 32]. Studies employing glucose tolerance testing have demonstrated prevalence of hypoglycemia as high as 72% [8] following bypass and as high as 33% after sleeve gastrectomy [6]. While provoked testing may not be physiologic, worrisome recent studies using continuous glucose monitoring demonstrate that unrecognized hypoglycemia is far more frequent. For example, glucose values <70 mg/dl occur 63 ± 23 minutes per day in post-bypass patients known to have hypoglycemia, and even 34 ± 22 minutes per day in completely asymptomatic post-bypass individuals [22]. A recent abstract demonstrated even more severe hypoglycemia, with glucose < 50 mg/dl for 21 minutes per 24 hours, with 36% of patients reporting concurrent symptoms [33]. Furthermore, Schauer and colleagues reported recently that 64% of post-bypass patients with a prior history of T2D had hypoglycemic episodes [1].

To meet the critical unmet needs for the treatment of patients with severe hypoglycemia following bariatric surgery, we aim to develop a novel closed-loop glucagon system (CLG) incorporating a novel, stable non-aqueous glucagon formulation together with an infusion pump system guided by real-time continuous glucose monitoring that is triggered by a hypoglycemia alert algorithm. This innovative approach will permit delivery of glucagon via a subcutaneous pump format and algorithm that can be personalized to the individual need and also allow use of more physiologic lower doses of glucagon, preventing "rebound" hyperglycemia and "roller-coaster" hypoglycemia.

In initial studies, we developed and optimized a system to use a stable glucagon formulation, physician-delivered with an infusion pump system, within an open-loop system guided by continuous glucose monitoring. As a first step, we analyzed data collected from clinically-indicated diagnostic continuous glucose monitoring system testing (iPRO CGMS) already obtained from patients enrolled in the Hypoglycemia Clinic at Joslin (CHS 2015-18). Extracted data, including continuous glucose monitoring sensor glucose values, age, gender, and body mass index, and food and activity logs, were used to develop computational algorithms to allow prediction of hypoglycemia. When data analysis and

modeling for development of the treatment algorithm were completed, patients were recruited for the first phase of an open label clinical study (CHS 2015-28). In this study, we tested our hypothesis that CGMS-derived recognition of hypoglycemia and rapid treatment with lower, more physiologic doses of glucagon using an open-loop pump system would be an effective strategy to reduce the frequency and severity of hypoglycemia in patients with PBH. As per protocol, we performed mixed meal tolerance testing in 5 individuals with PBH, monitoring both plasma glucose (YSI) and sensor glucose (Dexcom). In CHS 2015-28, we utilized an algorithm specifically developed by study team engineers (Harvard School of Engineering) after analysis and modeling of the postprandial glycemic time course in patients with PBH. **Figure 2A** illustrates the “post-bariatric hypoglycemia algorithm” which was developed to specifically predict hypoglycemia in the setting of the rapidly-changing glucose levels in the postprandial state in this patient population. This algorithm was used together with the “classic” algorithm” to predict hypoglycemia not associated with rapid prandial excursions (similar to that used for patients with type 1 diabetes)(**Figure 2B**). Sensor data successfully triggered alarms to the study physician, who then delivered a dose of glucagon via the pump (thus open loop).

Figure 2. Algorithms used to detect rapid changes in glucose and trigger alarms to study physician. A. PBH algorithm, combined with B. classic LGP* algorithm.

research unit. Prior to discharge, the plasma glucose (measured by YSI) must be between 80 and 200 mg/dL on the final two measurements, taken at least 30 minutes apart. If the plasma glucose is between 80 and 90 mg/dL then the CGM trend arrow must be either stable or increasing during the last 30 minutes of observation.

When the standard meal is consumed, the Omnipod® pump will be removed and the site will be assessed visually using the Draize scale. Prior to discharge, the sensors will be removed to permit analysis of timing of alerts and the site of the Omnipod insertion will be reassessed using the Draize scale.

Blood samples collected during this visit will be processed and stored at -80 for subsequent analysis of insulin, glucagon and incretin hormone levels to assess endogenous responses (vehicle delivery days) as well as post-bolus plasma levels (glucagon delivery days). The patient will be called by a study team member within 24 hours of the study visit to collect data for symptoms, glucose values, and any adverse events following study visit.

Between one to two weeks following visit day 3, patient will be scheduled for visit day 5.

Visit Day 4 (Optional): Two to three days prior to visit day 5, patient will have an **optional** visit day 4, during which two Dexcom sensors will be placed on the anterior abdominal wall. If the study team and patient are comfortable with sensor placement, sensor placement can occur at home instead, again 2-3 days before visit day 5. The time of sensor placement will be documented by a phone call by a member of the study team and the study physician will review the medication, food and activity recommendations in preparation for study visit 5.

Study Visit Day 5: Mixed Meal Testing: This visit will be identical to visit 3 with the exception that the patient will receive the other treatment (either vehicle or glucagon) during the mixed meal tolerance test when a hypoglycemic event is predicted by the controller algorithms. As with study visit day 3, the patient will be called by a study team member within 24 hours of the study visit to collect data to survey symptoms, glucose values and for any adverse events following study visit.

Part 2: Testing control system for sensor-guided delivery of glucagon via closed-loop system to prevent post-exercise hypoglycemia in patients with post-bariatric hypoglycemia

During these visits we will test the efficacy of pump therapy containing Xeris glucagon in the prevention and management of post-exercise hypoglycemia in up to 20 patients with PBH. If patients studied in Part 1 are recruited for Part 2, there will be at least a two-month interval between completion of Part 1 and initiation of Part 2.

Visit Day 1: Screening: We will recruit adult male or female patients with PBH from the hypoglycemia clinic at Joslin (directed by [name]). Patients will undergo a history and physical examination, with particular emphasis on inclusion and exclusion criteria. Blood and urine samples will be obtained for screening laboratory testing including hemoglobin A1c, CBC, comprehensive chemistry, urinalysis, and pregnancy test (if applicable). An electrocardiogram will be obtained and reviewed during the visit by the study physician. Consent forms will be reviewed in detail with potential participants. Patient comfort, skill, and independence with sensor insertion will be determined at this visit and reassessed at subsequent visits.

Visit Day 2 (Optional): CGM Sensor Placement: Two continuous glucose monitor sensors (Dexcom) will be placed on the anterior abdominal wall two days prior to visit 3 (to ensure sensor availability and calibration for subsequent visit day 3) and will be blinded during the intervals between patient visits. Participants will be provided a glucometer and instructed in both sensor insertion and calibration techniques. This visit, with sensor placement, may occur concurrent with visit 1 if visit 3 can be scheduled within 2 days of visit 1/2. Alternatively, this visit can be substituted with a phone call if the patient has prior experience with sensor insertion and calibration and is comfortable with this approach. During the call, a study physician will discuss what medications, activities and food adjustments need to be made in anticipation of visit day 3 and will record timing of the sensor placements.

Visit Day 3: Exercise Protocol: The exercise protocol to be employed [35] will consist of cycling on a stationary bicycle ergometer in the clinical research center. Subjects will be counseled to avoid vigorous exercise for 24 hours before testing. Participants will arrive in the morning after an overnight (>12 hour) fast. Two intravenous lines will be inserted for blood sampling and to provide intravenous access. Two plasma glucose values greater than 75 mg/dL used to calibrate the sensors will be required to initiate the exercise study visit. Placement of the Dexcom sensors will be verified, and calibration will be performed using at least 2 venous blood glucose samples (YSI) obtained 15 minutes apart. A Garmin Foot Pod accelerometer will be applied. An EKG will be obtained and reviewed by a licensed provider prior to initiation of exercise. An OmniPod® containing glucagon will be inserted, with settings to deliver a dose of 300 µg of glucagon when an alarm is triggered by the controller algorithms which predict a glucose value <75 mg/dl.

Vital signs, including pulse, blood pressure, heart rate, and oxygen saturation will be assessed at baseline and every 2.5 minutes during exercise. Two baseline blood samples will be obtained for measurement of plasma glucose (YSI) immediately, and for subsequent hormonal assays. At time 0, low intensity cycling will be initiated; at time 5 minutes, intensity will be increased at 1 minute intervals until patient reaches target heart rate and will be continued until patient is exhausted, maximum heart rate is reached ($220 - (\text{age} \times 0.7)$), or total duration of exercise of 15 minutes is achieved. After exercise is completed, the subject will be returned to the supine position, post-exercise labs will be drawn and glucose levels will be assessed every 10 minutes for up to 180 minutes. Additional labs including insulin, glucagon, and incretins will be drawn at 10, 30, 60, 90 and 120 minutes after exercise.

Exercise will be halted immediately if the participant develops chest pain or chest pressure, undue shortness of breath, hypotension, feelings of being unwell, signs of poor perfusion (e.g., lightheadedness, confusion, ataxia, pallor, cyanosis, nausea, cold and clammy skin, etc.), heart rate above the prespecified maximum heart rate of the subject (MHR), drop in systolic or diastolic blood pressure by more than 20 mm Hg as compared with baseline, or if the participant chooses to stop. In addition at any point during the study visit, if the participant develops severe nausea, abdominal pain or feels the need to stop, they will be able stop the procedure.

As in part 1, the closed-loop system will be set to use both the post-bariatric hypoglycemia algorithm and classic algorithm to predict hypoglycemia below a threshold of 75 mg/dl. Once a hypoglycemic event is predicted this will trigger a pump-delivered bolus of glucagon or vehicle, with the goal of preventing further decline in glucose values. If the sensor glucose value is ≤ 75 mg/dL then 6 units (equivalent volume to 300 µg of glucagon) of glucagon or vehicle will be delivered; if automated delivery of glucagon by the pump is not yet available at the time of these studies, manual dosing of the test compound will be performed by the study physician, as guided by the algorithm.

If the closed-loop system generates a second hypoglycemia alarm after a lockout period (15 minutes for sensor glucose ≤ 60 mg/dL and 30 minutes for >60 mg/dL), then the closed-loop system will deliver a second dose of study drug as noted in part 1.

Plasma glucose will be measured (YSI) at 5 minute intervals for 30 minutes and then every 15 minutes for two hours after treatment to ensure successful treatment. Glucagon and insulin levels will be analyzed concurrently at time of hypoglycemia prediction alarm as well as 30 minutes and 60 minutes following treatment bolus to determine the magnitude of increase above baseline. Lunch will be provided 120 minutes after glucagon treatment.

As in part 1, if the glucose level falls at or below 55 mg/dl (i.e. as a result of vehicle delivery on vehicle treatment days, inadequate trigger, or inadequate pump-delivered glucagon response), or if the patient develops neuroglycopenia or discomfort with signs and symptoms of hypoglycemia then the closed-loop system will be deactivated and the treatment protocol for clinically significant hypoglycemia will be initiated followed by administration of a standard lunch meal (as described in part 1).

Thirty minutes after glucagon treatment, the Omnipod® pump will be removed and the site will be assessed visually using the Draize scale. Following the standard lunch meal, venous blood glucose will

Approved by

JDC CHS

be monitored every 15 minutes for a minimum of 2 hours and then every 30 minutes until the time of discharge. The time of discharge will be set at 6 hours after the exercise is stopped to ensure stability prior to discharge from the clinical research unit. Prior to discharge, the plasma glucose (measured by YSI) must be between 80 and 200 mg/dL on the final two measurements, taken at least 30 minutes apart. If the plasma glucose is between 80 and 90 mg/dL then the CGM trend arrow must be either stable or increasing during the last 30 minutes of observation.

Prior to discharge, the sensors will be removed to permit analysis of timing of alerts and the site of the Omnipod insertion will be reassessed using the Draize scale. Accelerometry data will be used as an input for future integration and modification of the algorithm. Blood samples collected during this visit will be processed and stored at -80 for subsequent analysis of insulin, glucagon and incretin hormone levels in response to exercise and treatment. The patient will be called by a study team member within 24 hours of the study visit to collect data for symptoms, glucose values, and any adverse events following study visit.

Hardware Cleaning:

Equipment that touches intact skin will be cleaned prior to and after each use, using methods suggested by manufacturer, including Clorox Healthcare 35309 Germicidal Wipes.

Dexcom G4 Platinum Professional Transmitter Cleaning Procedure: The transmitter is the non-disposable piece inserted into the sensor which is attached to the subject. In brief, the investigator will sanitize his/her hands, and then put on gloves and goggles. The transmitter will be placed contact side down on an absorbent wipe. All surfaces of the transmitter will be wiped in two directions using a folded germicidal wipe (Clorox Healthcare®35309 Bleach Germicidal Wipes). A clean portion of the wipe will be used for second, third, and fourth wipes in both directions (total of 8 wipes for each area of the transmitter). The surface will be allowed to remain wet with the disinfectant for 3 minutes and dried on a nonporous surface. The transmitter will be placed into a beaker containing Clorox Healthcare Bleach Germicidal Cleaner Spray Solution for 1 minute and then rinsed under tap water for 10 seconds. The transmitter will be wiped with a low lint cloth until fully dry. Used wipes and gloves will be disposed, and hands will be washed. Equipment will be stored in a clean zipped bag.

Dexcom G4 Platinum Professional Receiver: This system requires the use of a receiver shield and its components to protect the receiver from contamination. Manufacturer's instructions will be followed, with the receiver shield removed after each patient use to help reduce the risk of contamination for health care team members or subsequent participants. The gloved investigator will wipe the receiver with the disinfectant wipes, allow it to dry, change gloves, and remove the shield components.

Omnipod Pump Receiver: The pump itself is a single-use equipment so will be discarded after each use. The receiver (PDM) will not be handled by the patient, but only by the investigator team members. The PDM will be thoroughly wiped on the surface by gloved personnel with the germicidal wipes after each use, and used wipes and gloves will be disposed.

The EPA registration number for the Clorox Healthcare 35309 Germicidal Wipes, 6 3/4 x 9, Unscented, 70/Canister is EPA 67619-12. This hospital-grade disinfectant is EPA-registered to kill a total of 51 microorganisms, including all ESKAPE pathogens (E. faecium, S. aureus, K. pneumonia, A. baumannii, P. aeruginosa, E. aerogenes) in 30 seconds, HIV in 30 seconds, hepatitis viruses and norovirus in one minute, and TB and C. difficile in three minutes.

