4. DATA ANALYSIS / SUBJECT SELECTION

Subject Selection:

Approximately 40 subjects may be screened for this study, assuming approximately 30% will not meet inclusion criteria, and assuming 20% dropout rate. The goal is for 20 subjects to complete Part 1 and Part 2 studies. To allow for potential drop-outs, 28 subjects will be randomized.

Data Analysis:

All subjects who have received at least one dose of glucagon will be included in the data analysis set. Adverse events, vital signs, physical examination, laboratory safety variables (Screening to Final Visit), EKG (Screening to Final Visit), and local tolerability data will be reviewed and summarized on an ongoing basis during the study to evaluate the safety of subjects. Safety data will be presented in tabular and/or graphical format and summarized descriptively, where appropriate.

Sensor and glucagon or vehicle delivery information will be collected and evaluated for specificity and response time.

Plasma glucagon concentrations will be analyzed by a validated LCMS method in a GLP compliant lab (Celerion, Inc. Lincoln, NE). Insulin and incretin plasma concentration profiles will be analyzed with a commercially available radioimmunoassay method (RIA, Millipore) and analyzed using repeated-measures ANOVA.

The primary endpoint for this study is prevention of meal or exercise-provoked hypoglycemia, defined as glucose levels below <65 mg/dl, compared to vehicle control. Secondary outcome measures will compare outcomes for glucagon versus vehicle infusions for the following metrics including: (1) prevention of severe hypoglycemia (defined as glucose levels below 60 mg/dl); (2) prevention of rebound hyperglycemia (defined as glucose levels above 180 mg/dl); (3) time in goal range (65-180 mg/dl), reported in minutes.

Success will be defined as meeting the primary endpoint in 12 of 20 participants. If this is not achieved, the algorithm will be revised, and an additional 5 participants may be recruited for additional study.

Data will be analyzed after 10 individuals have completed the paired analysis of response to glucagon vs. vehicle. At that time, power will be determined, and sample size will be adjusted if needed.

Local Interim Data Analysis/Data Monitoring Plan

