The purpose of this study is to evaluate a new approach for the treatment of post-bariatric hypoglycemia. This project is not designed to be of direct benefit to any individual subject, although it is hoped that through the knowledge gained from these studies there will be general benefit to persons with or at risk of development of PBH. Subjects enrolled in this study receive comprehensive medical evaluation. As such, risks are appropriate in relation to the potential significant benefits for the significant number of persons with or at risk for hypoglycemia after bariatric surgery. Thus, the potential benefits to society are likely to outweigh the risks to the individual subject.

6. **POSSIBLE RISKS:**

Risks regarding participation include risks associated with:

Glucagon: Administered in usual rescue dose of 1 mg intramuscularly, glucagon can cause nausea, vomiting, dizziness, and headache, as well as other less common complaints (listed in table below). The doses to be administered in the present study (300 µg) will be less than ½ the usual rescue dose (1 mg).

Likely (≥10 subjects out of 100)	Less Likely (3-9 subjects of	Rare (2 or fewer subjects out of 100)	
Dizziness	Asthenia	Abdominal pain	Pain
Headache	Palpitation	Back pain	Pharyngitis
Nausea	Sweating	Confusion	Pruritis/Rash
Vomiting	Thirst	Diarrhea	Syncope
	Vasodilation	Dyspepsia	Taste perversion

Nonaqueous glucagon is a formulation of glucagon which is stable at room temperature. Previous studies have demonstrated that adverse events were generally mild to moderate in nature and similar to known effects of glucagon. A prior study of mini-dose glucagon (Xeris protocol XSMP-201) used doses similar to those in the current study (0.075 mg, 0.15 mg, and 0.3 mg); the most frequent adverse event was burning sensation at the injection site (58-75% of patients). Mild-to-moderate nausea was observed at the highest dose only (33%), while numbness was observed at injection site in up to 17% of patients. In 2015-28, glucagon administration resulted in local stinging at the site, with no nausea or other side effects reported by patients.

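### The local reactions the plan expects are sensations, but the one site instrument named in the available text is a visual score, so burning and stinging may be under-recorded

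*Combined protocol and SAP*

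**What the plan says.** **Site assessment.** In Part 1 (mixed-meal visits 3 and 5), the pump is taken off at the standard meal and "the site will be assessed visually using the Draize scale". Before the participant leaves, "the site of the Omnipod insertion will be reassessed using the Draize scale". Part 2 uses the same scale at a different time: "Thirty minutes after glucagon treatment, the Omnipod® pump will be removed and the site will be assessed visually using the Draize scale", with a repeat before discharge.

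**Expected local reactions.** In section 6 (Possible Risks, Glucagon), the plan says of a prior mini-dose study at 0.075, 0.15 and 0.3 mg that "the most frequent adverse event was burning sensation at the injection site (58-75% of patients", and that "numbness was observed at injection site in up to 17% of patients". Of the predecessor study, CHS 2015-28, it says "glucagon administration resulted in local stinging at the site", without giving a rate.

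**Other routes for symptoms.** Section 6 (Protections Against Risk) has staff ask about side effects at every visit. In both parts a team member telephones within 24 hours about symptoms and adverse events after the visit. Section 6 (Glucagon Infusion System) places a study physician and nurse in the room.

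**Reporting.** Section 4 (Data Analysis) lists adverse events and local tolerability as separate items in one descriptive safety review: "local tolerability data will be reviewed and summarized on an ongoing basis".

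**The concern.** The instrument does not match the reaction. The Draize score is read by eye, whereas burning, stinging and numbness are felt and need leave nothing to see. The reading also comes some time after the bolus, when a brief sensation may have passed.

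In Part 1 each participant has one glucagon visit and one vehicle visit. That pairing could separate discomfort due to glucagon from discomfort due to the formulation or the infusion itself. The documents give no burning rate for vehicle, so this trial would have to supply it. The answer bears on a system intended for repeated pump delivery. If discomfort is recorded only when someone happens to mention it, the comparison rests on incomplete counts with no common severity measure.

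**Working it through.** The plan states no figure on this point, so there is none to reproduce. The check sets the reactions against the routes that could record them, then sizes possible under-counting.

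**1. When the site is read.** The Part 1 text on second alarms puts lunch 120 minutes after the first dose or 30 minutes after a second, whichever is later. The pump comes off at that meal, so the first reading is normally about 120 minutes or more after the first bolus. It could be sooner if treatment of low glucose brings the meal forward. In Part 2 it is 30 minutes after treatment.

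**2. What each route can record.**

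| Route | Can record a sensation? | Site item, severity scale or bolus timing stated? |
|---|---|---|
| Draize score | No, it is visual | Timing fixed by pump removal and discharge |
| Side-effect question at each visit | Yes | None stated |
| Call within 24 hours | Yes, but worded for the time after the visit | None stated |
| Staff in the room | Yes, if mentioned | None stated |

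**3. Expected number affected.** Inputs: 20 completers (section 4); burning 0.58 to 0.75 and numbness up to 0.17 (section 6). Assumptions: injection rates carry over to pump delivery, and all 20 receive a glucagon bolus.

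- Burning: 20 × 0.58 = 11.6 to 20 × 0.75 = 15.0.
- Numbness: up to 20 × 0.17 = 3.4.

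**4. Effect of incomplete capture.** Let q be the share of burning events that open questioning records. The documents give no value, so a range is shown. Expected reports = 20 × p × q. Chance of at least one report = 1 − (1 − p × q)^20, treating participants as independent.

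| q (assumed) | Expected reports of 20 | Chance of at least one |
|---|---|---|
| 1 | 11.6 to 15.0 | above 99.9% |
| 0.5 | 5.8 to 7.5 | 99.9% or more |
| 0.25 | 2.9 to 3.8 | 96% to 98% |
| 0.1 | 1.2 to 1.5 | 70% to 79% |

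For example, at p = 0.58 and q = 0.1: 1 − (1 − 0.058)^20 = 0.697.

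**5. Effect on the comparison.** If q is the same on both days, the observed difference in burning rates is q × (glucagon rate − vehicle rate). At q = 0.25 it shrinks to a quarter of the true difference. If q differs between days, the error can go either way.

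Burning is therefore unlikely to be missing from the safety data, but its count and the paired difference could be well below the truth.

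**The case against.** A reader might infer that the safety summary will look benign. The documents do not support that. Adverse events are summarised in the same safety review as local tolerability, the plan itself classes burning as an adverse event, and stinging was reported from the predecessor study. Even at one-in-ten capture, at least one report is more likely than not.

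A reader might also infer that the trial cannot show a glucagon-vehicle difference. That is too strong for Part 1: each meal visit delivers one treatment, so a side effect reported there can be attributed by visit without timing it to the bolus. Nor do the documents say that adverse events go ungraded; they state no scale.

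Finally, it cannot be claimed that no sensory measure exists anywhere. The opening of the document and the first-bolus part of the Part 1 visit, with Table 1, are not in the available text, and a symptom rating could sit there.

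Other fair objections: the 58-75% comes from injections at three doses, not a pump; a bolus depends on an alarm, so not everyone need receive one; and local tolerability is neither a primary nor a secondary outcome. These limit the size and weight of the point. They do not remove the mismatch between a visual score and a felt reaction.

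**Conclusion.** The point holds as a minor one. In the available text, sensory site reactions have no prompted item, stated severity scale or timing relative to the bolus, and the one named site instrument cannot record them. They would probably appear among adverse events, but their frequency, severity and glucagon-vehicle difference may be understated.

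The size, about 12 to 15 of 20 with burning, rests on the earlier injection rates carrying over and on all 20 receiving glucagon. With n participants dosed it becomes 0.58n to 0.75n. How much would go unrecorded is unknown, because the capture share is assumed throughout. No planned efficacy conclusion is affected. If the missing Part 1 text already contains a site-discomfort rating, the point falls away to that extent.

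**What to change.** Keep the Draize readings. Add a 0-10 burning/pain rating and a yes/no numbness question soon after each bolus and again at pump removal, in the same words and at the same times on glucagon and vehicle days. Tabulate both by treatment beside the Draize score, and report the within-participant glucagon-vehicle difference from Part 1, where the pairing is clearest.

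The cost is small. Two items at two times make 4 case-report entries for a visit with one bolus, and 2 × 2 + 2 = 6 for a visit with two. Staff already in the room can ask, although the first rating falls within the 5-minute glucose sampling. Prompting may raise reporting; asking identically on both days should spread that over both treatments. No dose, schedule or clinical rule changes.
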